4.2.2.3 Demographics and risk factors

Risk factors for severe pneumonia will be collected from each case and control. These data will be used to control for confounding in the case control analysis, to describe the epidemiologic setting of the sites and to inform the global projection models. Furthermore, other putative risk factors for severe pneumonia will be assessed by examining their occurrence among cases compared with controls. The case control analysis for causal inference assumes that controls represent the population from which cases are derived. We will obtain demographic data, information on socio-economic status and access to health care, to assess this assumption. Case and control health care records may be reviewed to obtain some of this data (e.g. immunization history, ARV treatment history, current/previous enrollment in another study, and CD4 counts if HIV-positive).

Table VI. Risk Fa	ctors*		
Category	Risk factor /Variable	Category	Risk factor/Variable
Demographic	Age	Co-morbidities/	Diarrhea
	Sex	intervention	Sickle Cell Disease
	Mortality status of		Prematurity
	Mother/Father		
	Maternal age		Anemia
	Father's education		Antibiotic use
	level		
	Maternal literacy		Steroid treatment
	Race/Ethnicity		Birth weight
Nutrition	Breastfeeding		
	Vitamin A		
	supplementation		
		Family	Rural or urban residence
	Zinc	environment	Number of siblings
	supplementation		
			Type of home
			(compound/single
			family) Sex of siblings
			Sex of siblings
			Age of siblings
	Vitamin D status		Number of children
	(lab test on stored samples)		living under one roof
	Malnutrition: will be assessed by z		Birth order
	score from weight		Number of people in the
	and height;		family
	Pedal edema	1	Temporary guests in the
			household
			Out-of-home care
Vaccination	BCG		
history			Ventilation in the main
	DPT3 Measles	-	living area Smoker in the house
	HiB		Maternal smoking

Table VI. Risk Fact	ors*		
Category	Risk factor /Variable	Category	Risk factor/Variable
	PCV		Urinary cotinine levels in child (lab test)
	Influenza		Child being carried on mother's back while cooking
	Rotavirus		Type of cooking fuel
Co-morbidities/ intervention	Cold/ hypothermia (temp. threshold to be defined)		Type of stove
	Malaria Parasitemia (lab	Socio-economic status	Maternal Education
	test) Bednet ownership		Head of Household occupation
	and use		Household Income
	HIV infection status		Source of water in the house
	AIDS		Types of wall
	ARV treatment		Household possession

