4.5.1.6 Urine

Urine samples will be collected from cases and controls for two purposes: (i) to examine for the presence or absence of antibiotic activity, a marker of recent administration of antibiotics which might influence the sensitivity of culture-based microbiological techniques and (ii) to be stored for future examination of antigens that determine etiology and relevant urinary biomarkers (e.g. biomarkers of smoke/air pollution exposure and urinary arsenic). Urine will be taken at the

Version 6.0_15Nov2013

earliest opportunity from children admitted as cases, ideally before the first dose of antibiotic therapy. However, antibiotic infusions will not be delayed to obtain a urine sample uncontaminated with hospital-administered antibiotics. If the urine specimen is not obtained by this time, antibiotic administration should begin. The specimen can still be collected and analyzed for detection of antigens.

For infants and young children, urine will be collected into a perineal adhesive bag and transferred to a sterile universal container. Older children may pass urine directly into a sterile universal container. If antibiotics have been given by the nursing or medical staff prior to capturing the specimen then the specimen data collection form will be documented appropriately and the sample container will also be marked. Samples will be taken to the laboratory and stored immediately at 4-8 °C until processed.

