6.2 Analysis plan for each objective

6.2.1 Determine the association between pneumonia and infection with known putative viral, bacterial, mycobacterial and fungal pathogens

The basic structure of the analytic problem is pictured in Figure 5 below. There are a set of risk factors or other attributes (denoted "X") of children that influence the risk of being infected (denoted "I") with a given pathogen. We cannot know in truth whether children are truly infected, but we infer this based on a series of laboratory measurements ("M") which include among others, for example, multiplex PCR of nasal secretions, culture of blood for bacterial pathogens, and assessment of induced sputum for acid fast bacilli. Among the infections children have, only some of these pathogens are causally linked to their disease, namely hospitalized, severe pneumonia (denoted as "Y").

[Note: For the sake of simplicity we will use "30" pathogens as an example of how many different individual pathogens we will identify in PERCH and we use "40" as an example of how many lab measurements there are. These numbers are approximations of the number of pathogens that can be identified or the number of lab measurements being collected, and are merely place holders for the sake of clarity. Also, one of the "pathogens" is the "no pathogen identified" category that is relevant to future pathogen discovery efforts.]

Figure VII. Basic structure of the measurement of and relationship between infection and disease in cases

PERCH Protocol

The key features of this formulation of the epidemiologic problem include the following:

[figure not shown]
- Infection status is a binary indicator for each of the 30 pathogens that can be measured, plus one additional broad category that includes "all others that are not identified by the lab testing". As there are 31 binary indicators of infection status for each child, there are 2³¹ (i.e., over 2 billion) possible infection states (i.e. infected or not infected for each of 31 "pathogens"). This enormous number of possible infection states, most of which have 0 people in them, creates statistical and modeling complexity which must be addressed. Below we discuss ways of reducing this dimension by smoothing (aggregating) across the "neighboring" cells to make estimation feasible.

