- 2. Risk factors for infection with a given pathogen, including among other variables age, vaccination status, socioeconomic status, nutritional status, HIV infection, and antibiotic use are allowed to affect the risk of having each of the 30+1 infections. Some of these risk factors may also affect the general probability of developing 'hospitalized pneumonia' by a pathway other than the specific infection, for example, by reducing access to medical care.
- 3. Hospitalized, severe pneumonia is caused by one or more of the 30+1 pathogens causing infection and possibly by two-way interactions between them.
- We do not directly observe the presence of each infection. Rather the presence of infection by each pathogen must be inferred from up to 40 laboratory test results ("M") (illustrated in Table XII).

Table XII. Determination of infection status for30 pathogens using results from 40 lab tests						
Path 1 Path 2 Path 30						
Lab test 1	infected	NA	NA			
Lab test 2	NA	infected				
Lab test 40	Infected	Infected	NA			

5. The sensitivity and specificity of each laboratory test will be represented by a distribution on (0,1) (i.e., estimates of sensitivity and specificity can range from >0% up to and including 100%). Information from existing literature on the laboratory assays will be used to estimate their sensitivity and specificity. Uncertainty bounds around the sensitivity and specificity measures of the lab tests will be incorporated.

Data analysis ignoring measurement error. If the infection status for each of the 30 pathogens was known for each pneumonia case and for controls, the approach to analysis would have two parts, denoted A, in red, and B, in green, in Figure 6 below.

Figure VIII. Analysis approach

In Part A, among the cases and among the controls we will regress the presence/absence of infection for each pathogen on risk factors. The co-occurrence of infections would be of particular interest. We will therefore estimate the pairwise odds ratio for each of the 30 choose 2 = 435 pairs of infections, focusing on a smaller subset (e.g. top 30) with substantial prevalence. *Using marginal models* (e.g. Diggle, Heagerty, Liang and Zeger, 2002), the odds ratios could be regressed on covariates to build an understanding of what factors (e.g. age, nutritional status, vaccination status) influence the co-occurrence of pairs of infections (Diggle PJ 2002).

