Measurement error: The main challenge is that infection status will not be observed exactly for any child. Rather a series of laboratory test results will provide noisy evidence about each infection. For each test, there will be some degree of prior knowledge about its sensitivity and specificity. *A measurement error model* will be included in the analysis as represented by Part C in Figure 6 above.

We will consider two approaches for incorporating measurement error. In the first we will assume that the lab test results are independent of one another. We will use the external knowledge about sensitivity and specificity to set prior distributions for each. The joint probability distribution of the unknown infection status of a child will be inferred from the test results given the child's values of X and Y. We will only infer the univariate and bivariate marginal distributions. It will be possible to infer the class probabilities in the latent class version.

This approach ignores the likely correlation among test results that use the same body fluid or extraction process. We will extend the independence model by allowing for fluid and extraction "errors" that cause all of their test results to be corrupted (usually toward zero).

Approach to analysis: Once the measurement error is acknowledged, analysis will be implemented *using a Bayesian hierarchical model and Markov chain Monte Carlo (MCMC) methods of inference*. We will repeatedly simulate from the conditional distributions of the infection statuses (I) and the model parameters given the observable (X, Y, M). The histograms that are the target of inference will be constructed, with uncertainty, by summarizing the distribution of the I's and of the I's from the analysis. In the first months of the project, the detailed specification of the hierarchical model will be developed and tested on simulated data.

6.2.2 Estimate the fraction of pneumonia attributable to pathogens for which vaccines are currently under development

(See section 6.2.1. above).

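### The etiology model lets antibiotic use change the risk of infection but not the sensitivity of culture, so culture-detected bacteria may be under-attributed in pre-treated children

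*Protocol*

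**What the plan says.** Section 6.2.1 of the protocol separates child attributes (X), true infection (I), laboratory measurements (M) and pneumonia (Y). Three statements fix how antibiotics and test error enter.

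- Item 2, on the X attributes: "nutritional status, HIV infection, and antibiotic use are allowed to affect the risk of having each of the 30+1 infections".
- Item 5, on test error: "Information from existing literature on the laboratory assays will be used to estimate their sensitivity and specificity". Uncertainty bounds are to be carried along.
- The measurement-error paragraphs: "We will use the external knowledge about sensitivity and specificity to set prior distributions for each". The one extension named is for errors shared by a body fluid or an extraction process.

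Section 4.5.1.6 explains why urine is tested for antibiotic activity. It calls this activity "a marker of recent administration of antibiotics which might influence the sensitivity of culture-based microbiological techniques".

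Section 4.2.2.3 says of the risk-factor data: "These data will be used to control for confounding in the case control analysis". Table VI lists antibiotic use among those factors and does not say whether it means use before the illness or for it.

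**The concern.** Section 4.5.1.6 describes an effect of antibiotics on the measurement: an infected child is less likely to have a positive culture. The model text gives antibiotics a path to infection only. When sensitivity is the same for exposed and unexposed children, a lower culture yield among the exposed has one place to go, a lower prevalence of infection in that group. Fluid and extraction errors do not cover this, because antibiotic exposure belongs to the child and affects cultures from several specimens at once.

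The pathogen-specific fraction of pneumonia is a primary objective (section 2.1), and sections 6.3 and 6.3.3 plan site-specific and between-site analyses. If pre-treatment differs between sites, a difference in care before admission could be reported as a difference in etiology.

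**Working it through.** The protocol states no pre-treatment share, no culture sensitivity and no size of antibiotic effect, so there is no figure to reproduce. All numerical inputs below are assumptions unless marked otherwise.

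**Notation.** π is the true prevalence of a bacterial infection, taken as equal in exposed and unexposed children. s is culture sensitivity in unexposed children, r the relative sensitivity after antibiotics, and q the share exposed. Specificity is 1, there is one culture test, and sensitivity is held at its prior value.

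**1. Priors that describe untreated children.** Expected positivity is πs in unexposed and πsr in exposed children. Dividing both by the common s gives π and πr. The pooled estimate is (1 − q)π + qπr = π[1 − q(1 − r)], so the relative shortfall is q(1 − r). s cancels.

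| q | r = 0.7 | r = 0.5 | r = 0.3 |
|---|---|---|---|
| 20% | 6% | 10% | 14% |
| 40% | 12% | 20% | 28% |
| 60% | 18% | 30% | 42% |

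With π = 10%, q = 40%, r = 0.5, the estimate is 10% × (1 − 0.4 × 0.5) = 8.0%. With sensitivity sr used for exposed children, it is 0.6 × 10% + 0.4 × 10% = 10.0%.

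**2. One exposed child with a negative culture** (π = 10%, s = 0.6, r = 0.5). The true probability of infection is 0.10 × (1 − 0.30)/(1 − 0.10 × 0.30) = 0.070/0.970 = 7.2%. The common-sensitivity model uses prevalence 5% and sensitivity 0.6: 0.05 × 0.4/(1 − 0.05 × 0.6) = 0.020/0.970 = 2.1%. The allowance for a false negative is too small, but it is not zero.

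**3. Priors that match the study's average mix.** The common sensitivity is then s[1 − q(1 − r)], and the pooled estimate returns to π = 10.0%. There is no overall bias, only a wrong split between exposed and unexposed children.

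**4. The same prior applied to two sites.** Take two equal-sized sites, both with π = 10%, q = 20% and 60%, and r = 0.5. The average q is 40%, so the common sensitivity is 0.8s. The first site gives 10% × 0.9/0.8 = 11.25%; the second gives 10% × 0.7/0.8 = 8.75%. The pooled value is right, while two identical sites appear to differ.

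**5. Cases against controls.** The only culture planned for controls is nasopharyngeal culture for pneumococcus (Tables VIII and X), so this step is limited to that test. From section 6.3.3.1, take 15% positivity in cases and an odds ratio of 2.0, which implies 8.11% in controls. Assume that these are the values without antibiotics, that 40% of cases and 5% of controls are exposed, and that r = 0.5. Cases become 15% × 0.80 = 12.0% and controls 8.11% × 0.975 = 7.91%. The odds ratio is (0.120/0.880)/(0.0791/0.9209) = 1.59.

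**The case against.** The strongest reply is that a single common sensitivity is partly inferred from silence. The same section defers the detailed hierarchical model to later work on simulated data, and a SAP may settle the matter. The model diagrams (Figures VII and VIII) are not reproduced in the text consulted, so a drawn path from X to M cannot be excluded. This limits certainty. It does not remove the point: the prose assigns antibiotics a role, names the source of sensitivity and names one extension, and none of these carries the effect that section 4.5.1.6 describes.

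The protocol also plainly recognises the problem. It aims to take respiratory specimens before hospital antibiotics (section 4.1.2), restricts bacteriology on late induced sputum (4.5.1.5), tests for antibiotic activity and lists antibiotic pre-treatment as a likely subgroup (6.3). These steps help, but they do not reach antibiotics taken before admission. A subgroup analysed with the same common sensitivity would show the pattern without correcting it. Stratification by pre-hospital antibiotics is stated only for antimicrobial resistance (6.2.5).

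Four stronger readings are tempting, and the text does not support them:

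- *Suppressed bacteria are read as truly absent.* Infection is latent and inferred with imperfect sensitivity, as step 2 shows.
- *The bacterial fraction is necessarily biased down.* Step 3 shows no pooled bias if the priors match the study mix. Section 4.5.1.6 names culture only, and Table V also plans PCR and antigen evidence.
- *Antibiotic use should not be in X.* Antibiotics may truly clear or suppress carriage, so a path to infection is reasonable. Any such true effect would also make the shortfall in step 1 smaller.
- *The case-control contrast will be adjusted for antibiotics given for the current illness.* Sections 4.2.2.3 and Table VI leave that open, but Part B of section 6.2.1 names only infection indicators and selected interactions as predictors.

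**Conclusion.** The point holds in a conditional form. The text places antibiotic exposure on the infection side only and leaves it out of the measurement model, against the protocol's own account of what antibiotics do to culture. If the sensitivity priors reflect mostly untreated children, culture-detected bacteria are under-attributed, by 6-42% in relative terms for assumed pre-treated shares of 20-60% and relative sensitivity of 0.3-0.7. The effect on the whole bacterial fraction is smaller wherever PCR or antigen results contribute. If the priors match the average mix, the pooled fraction can be right, but one value per test still distorts contrasts between sites, or between cases and controls, with different pre-treatment. The structural gap rests on the protocol's wording. The size rests entirely on assumptions, and joint fitting with other tests could move it.

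**What to change.** In item 5 and the measurement-error paragraphs of section 6.2.1, let the sensitivity of culture-based bacterial tests depend on antibiotic exposure before the specimen was taken. Define exposure from history and from the serum and urine antibiotic activity already planned, with urine collected after hospital antibiotics identified as such. Use a prior under which sensitivity is no higher in exposed children. Add a sensitivity analysis restricted to unexposed children. Antibiotic use may stay in X.

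In section 4.2.2.3, state that when Table VI data are used to control confounding in the case-control analysis, antibiotics given for the current illness are not adjusted for, since they are a consequence of that illness. History is needed here, because an activity assay cannot date use relative to illness onset.

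The cost is model wording and code. Serum activity is listed for cases and controls in Tables IX and X, so no new specimen is needed; urine activity is planned only on a subset or as resources permit. Intervals for bacterial fractions will be somewhat wider, and separating an effect on infection from an effect on sensitivity will rely on the priors, which should therefore be reported and varied.

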6.2.3 Analysis of risk factors for pneumonia for etiology specific causes of pneumonia

The proportion with the risk factor in cases and controls, and between etiologies among cases, will be compared using χ^2 and Fisher's exact test as appropriate. Continuous data will be

compared using *t* test or Kruskal-Wallis rank sum test. Multivariable logistic regression will be used to adjust for other risk factors and to assess interactions between risk factors and etiologies.

All patient information related to severity will be considered and logistic regression will be used to identify putative indicators of severity by associating them with fatal cases.

6.2.4 Develop a severity index and use to assess association between etiology and severity

Putative indicators of severity at admission will be identified by associating them with fatal cases. Logistic regression will be used to determine the association between the indicators of severity (e.g., hypoxemia, chest wall indrawing, cyanosis, etc.) and severe outcomes of pneumonia (immediate (in-hospital) death, death after leaving hospital, and duration of hospital stay among those who did not die). A severity index will be developed (such as a score from 1=less severe to 7=death). Latent class analysis will be explored for its potential to distinguish severity classes of cases. For developing the index, all patient information related to severity will be considered independent of etiology. The distribution of the severity index among the etiologies will then described. Pairwise comparisons of the severity index between etiologies will be tested using 2 x n χ^2 or Fisher's exact test.

6.2.5 Determine patterns of antimicrobial resistance.

The proportion of invasive isolates resistant to antibiotics will be estimated for important pneumonia pathogens including *M. tuberculosis, S. aureus, Salmonellae* spp. and others such as *Klebsiella pneumoniae* and *Pseudomonas aeruginosa*. Frequencies of susceptibility by pathogen and antimicrobial will be generated. Analyses will be stratified by pre-hospital exposure to antibiotics. The proportion of isolates that are resistant to multiple antimicrobials will also be calculated.

6.2.6 Determine the association between pneumonia etiologies and digital chest auscultation, with and without chest radiography

Logistic regression will be used to determine the association between the breath sounds (wheeze, crepitations, stridor, no sounds) and etiology, stratified by CXR findings (e.g., alveolar consolidation, otherwise abnormal, normal). The distribution of the breath sounds (and CXR findings) for each etiology will be described. Pairwise comparisons of breath sounds between etiologies will be tested using 2 x n χ^2 or Fisher's exact test.

6.3 Sample size and power calculations

Over two years, the PERCH study aims to enroll 5000-7000 patients with severe or very severe pneumonia and approximately an equal number of controls. The study will be conducted using a standardized methodology that will facilitate pooled analysis. This sample size will represent probably the largest multi-center pneumonia etiology study in children in recent times. This surpasses even the BOSTID studies in the 1980s, which included 12 sites and nearly 4000 hospitalized episodes of lower respiratory tract infection. As such, the study is expected to provide substantial power to detect new etiologies of pneumonia, to offer improved precision on existing estimates, and in case-control comparisons, to determine associations with risk factors that may not have been possible previously.

The large study size will allow for many stratified or subgroup analyses. Because differences in epidemiologic and environmental factors between sites or between risk groups may result in differences in the distribution of the pathogens, power calculations are provided for a range of sample sizes for likely site-specific and sub-group analyses, as well as overall.

Likely sub-group analyses include:

- HIV status
- antibiotic pre-treated
- disease severity
- symptomatic vs. asymptomatic controls
- age
- presence of an epidemic such as H1N1
- season
- year
- particular pathogens (for pathogen-specific risk factor analysis)
- malaria
- sickle cell disease
- fatal cases
- other risk groups (e.g., Vitamin D deficient, malnourished, low SES, etc.)
- specimens in limited quantify such as lung taps or post-mortem lung biopsies

The main drivers of the number of cases enrolled will be the requirement to provide a reasonably specified description of pneumonia etiology at seven different sites representing different socio-epidemiological settings. Each site varies in the number of cases eligible for enrollment. Table 13 summarizes the number of cases that will likely meet the PERCH case definition and would consent to be enrolled at each site. Estimates are conservative.

Number of available cases per site and overall

Table XIII summarizes the number of cases that will likely meet the PERCH case definition and consent to be enrolled at each site.

Table XIII. Estimated total number of eligible, consenting severe and very severe casesavailable for enrollment/analysis over 2 years.					
		2-year enr	ollment potential		
Site	Total Severe* Very severe				
	cases				
Bamako, Mali	700	525	175		
Basse, The Gambia	1170	1016	154		
Sa Kaeo/Nakhon	500	400	100		
Phanom, Thailand					
Soweto/Johannesburg,	2000	1460	540		
South Africa					
Dhaka, Bangladesh	3000	2250	750		

Kilifi, Kenya	1800	1440	360
Lusaka, Zambia	3400	2000	1400
Total	12570	9091	3479

*For sites with unknown ratio of severe to very severe, 25% very severe was assumed.

